Therapist perceptions of treatment response. To assess *Therapist-Perceived Effectiveness*, therapists will be asked on a 7-point scale at posttreatment: "How effective do you think the program was for treating this child?" [0=very *ineffective*; 3=*somewhat effective*; 6=very *effective*]. In addition, after each treatment session (for Therapist-Led CBT cases) or check-in call session (for Guided Online CBT cases), therapists will complete the *CGI-I*^{122,129} to characterize their session-by-session judgement of the extent of treatment-related improvement, relative to the child's baseline presentation. Therapists will again complete a CGI-I at posttreatment.

7.6.3 Treatment variables. Treatment variables assessed in the Kids FACE FEARS trial focus on treatment preferences and expectancies, the scope and content of each session and check-in call, treatment fit and flexibility, treatment engagement and barriers, and therapeutic alliance. Table 5 presents a summary of the treatment variables assessed, which are described in detail below.

Table 5. Treatment Variables in the Kids FACE FEARS Trial

Domain	Measure	Informant(s)	Assessment Point			
			Baseline	After First Session	After Each Session	Midtreatment
Treatment Preferences and Expectancies						
Treatment Preference	Treatment Preferences & Expectancies Survey	CS, Y	X			
Anticipated Treatment Comfort	Treatment Preferences & Expectancies Survey	CS, Y	X			
Anticipated Treatment Comprehension Difficulties	Treatment Preferences & Expectancies Survey	CS, Y	X			
Anticipated Treatment Scheduling Difficulties	Treatment Preferences & Expectancies Survey	CS, Y	X			
Therapist-Anticipated Treatment Effectiveness	Early Treatment Expectations Form	T		X		
Therapist-Anticipated Participatory Engagement	Early Treatment Expectations Form	T		X		
Therapist-Anticipated Therapeutic Alliance	Early Treatment Expectations Form	T		X		
Therapist Case-Specific Self-Efficacy	Early Treatment Expectations Form	T		X		
Scope and content of treatment sessions/check-in calls	Session Summary Form	T			X	
Treatment Fit and Flexibility	Session Summary Form	T			X	
Treatment Engagement and Barriers						
Attendance	Administrative Data	A			X	
Homework engagement	Session Summary Form	T			X	

Treatment completion	Administrative Data	T	X
Child participatory engagement	Session Summary Form	T	X
Caregiver participatory engagement	Session Summary Form	T	X
Comprehension difficulties	Treatment Barriers Survey	CS, Y	X X

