7.15.4 Retention and Study Compensation

Based on similar studies conducted in usual care settings that do not provide free study treatment, we expect roughly 30-50% attrition by the final follow-up timepoint, and roughly 10% of data points to be missing with each collected timepoint. REDCap surveys will be configured to minimize missing values (e.g., requiring participants to complete each item, or explicitly indicate “refuse to answer” before proceeding to the next item; providing real time alerts to the data management team when items or entire forms are missing). Data will additionally be checked on a weekly basis by a research supervisor, and patterns of missingness will be identified and corrected in real time throughout the study. To further reduce instances of missing data, we have kept the number of study forms to a minimum in order to minimize the burden to participants, and participants will be provided compensation for their time completing study forms. Finally, participants will be compensated for the burdens of completing study assessments (see below).

Given the aim to evaluate treatment engagement and performance under typical circumstances, families are not compensated for participating in treatment. To ensure generalizability and observe the treatment comparators under natural conditions, treatment is not funded by the study nor offered for free. Rather, treatment is to be paid for via the natural channels of payment in the participating health centers (e.g., insurance and co-payments). In contrast, families are compensated for participation in study assessments that are not part of the treatment comparators under study. Specifically, families will receive the following compensations for completing various study assessment components:

- a. \$50 for baseline assessment (staggered payments: \$25 following baseline questionnaires and \$25 following baseline PARS completion)
- b. \$25 for midtreatment assessment
- c. \$50 for posttreatment assessment
 - i. \$30 additional compensation for completing posttreatment PARS assessment
- d. \$100 for completing follow-up assessment

*Coaches (who are not guardians) will not receive compensation for the assessments they complete. Compensation will only be provided to the youth and guardian informants. One ClinCard that will be loaded with the above payments will be given to each family for each child enrolled in the study.

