7.16.2 Handling of Missing Data

7.16.2.1 Prevention and monitoring. All study data will be collected via electronic capture and communication directly with the study team. Based on similar studies conducted by our group and in related research in similar settings, we expect roughly 10% of data points to be missing. REDCap surveys will be configured to minimize missing values (e.g., requiring participants to complete each item, or explicitly indicate "refuse to answer" before proceeding to the next item; providing real time alerts to the data management team when items or entire forms are missing). Data will additionally be checked on a weekly basis by a research supervisor, and patterns of missingness will be identified and corrected in real time throughout the study. To further reduce instances of missing data, we have kept the number of study forms to a minimum in order to minimize the burden to participants, and participants will be provided compensation for their time completing study forms. Finally, participants will be compensated for the burdens of completing study assessments at a rate of \$50 for baseline assessments (including PARS) and, \$25 for midtreatment assessments, \$50 for posttreatment assessments (including PARS), \$100 for week 52 assessments and \$30 for completion of PARS at posttreatment (note: compensation will not be provided for completion of measures that will be included as part of routine care). Coaches will not receive compensation for the assessments they complete.

7.16.2.2 Statistical handling of missing data. All analyses will consist of intention-to-treat models drawing on all available data. To account for missing data, we will employ multiple imputation. Recommended procedures for single and multilevel multiple imputation will be conducted using BLIMP software, using fully conditional specification multiple imputation (FCS-MI). For each model, 50 datasets with imputed values will be created using other model covariates as predictors of missingness. Model convergence will be assessed across 8 Markov Chain Monte Carlo (MCM) processes and verified for potential scale reduction (PSR) factor<1.05. Main analyses will be conducted on the imputed dataset and the results will be pulled for final estimates (using R 4.4.1 mitml for imputation pooling per Rubin's rules, and lme4 for multilevel models, or lm and glm for linear and logistic regression models).

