7.16.3 Covariates

Covariates for each model will include site, language of care, youth age, youth gender, youth race, youth ethnicity, and family resource insecurity (see Measures)

7.16.4 Primary analyses: Comparative effectiveness analyses. For primary analyses on continuous outcomes that were measured across the 4 major timepoints (e.g., caregiver- and youth-reports on the PROMIS Anxiety Scale, CALIS), mixed models of change¹⁴⁴ will be run separately for each outcome. Mixed models are preferred for longitudinal designs because they allow for individual estimates of change and have robust power in the presence of missing data and attrition.^{145,146} Covariates for each model will include site, language of care, youth age, youth gender, youth race, youth ethnicity, and family resource insecurity (see Measures), and any other baseline variables found to significantly differ across participants in the two conditions. The random effects of intercept (reflecting individual variation in mean outcome level) will be assessed. The fixed effects of Treatment Condition, Time, and the Treatment \times Time interaction will be analyzed in the prediction of change. We will examine non-linear models of change (i.e., log transformations of Time), which afford examination of symptom trajectories across time that are not gradual and incremental (e.g., steep improvements during initial weeks of treatment, followed by a slowing down of improvements toward the end of treatment, and then relative stability across the follow-up time interval). To aid interpretation of the meaningfulness of between-group differences, Cohen's d 's will be computed for each continuous outcome on model means at post and follow-up.

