For primary analyses on the dichotomous categorical outcomes PARS Treatment Responder Status at posttreatment, baseline PARS scores will be examined for each participant to determine their individual thresholds for classification as Treatment Responders (i.e., 35% PARS score reduction). These thresholds will be used to classify each participant's statuses as posttreatment. Logistic regression models will examine Treatment Condition (along with the study covariates) as a predictor of Treatment Responder Status and Remission Status at post. For primary analyses on continuous outcomes of Treatment Satisfaction at post, linear regression models will examine Treatment Condition (with the study covariates) as a predictor of caregiver- and youth-reported posttreatment satisfaction.

7.16.5 Heterogeneity of treatment effects. For Aim II analyses (heterogeneity of treatment effects) predictor and moderator terms will be added to the models predicting youth anxiety severity that were outlined above. For study covariates being considered as predictors/moderators (e.g., language of care, youth age, youth gender, youth race, youth ethnicity, and family resource security), this will entail only adding interaction terms, as the main effects of these variables will already be in the models. For the additional variables considered as treatment moderators that are not already included as model covariates (e.g., caregiver nativity) this will entail adding main effects and interaction terms to the models. For each model examining heterogeneity of treatment effects, the relevant terms of interest will be the 2-way interaction of Variable \times Time (reflecting whether the variable uniformly predicted change across the two treatments) and the 3-way interaction of Variable \times Treatment Condition \times Time (reflecting whether the variable moderated treatment effects; i.e., whether the variable predicted differential response across the treatments). As with the Aim I comparative effectiveness analyses, log transformations of Time will be entered to consider non-linear models of change. Significant interactions will be followed up with post-hoc probing on subgroups to clarify the nature and direction of interaction, and results will be plotted for visual depiction.

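### The imputation rule names no auxiliary variables and leaves the handling of product terms open, although 30-50% attrition by Week 52 is expected

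*Combined protocol and SAP*

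**What the plan says.** **Imputation.** Section 7.16.2.2 plans fully conditional specification multiple imputation in BLIMP, single-level and multilevel. It is rebuilt for every analysis: "For each model, 50 datasets with imputed values will be created", "using other model covariates as predictors of missingness".

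**Covariates.** Section 7.16.3 states: "Covariates for each model will include site, language of care, youth age, youth gender, youth race, youth ethnicity, and family resource insecurity". Section 7.16.4 adds "any other baseline variables found to significantly differ across participants in the two conditions". It lists Treatment Condition, Time and their interaction separately, as fixed effects. The PARS responder and satisfaction models contain arm and the study covariates.

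**Moderators.** Section 7.16.5 adds a three-way term with arm and time, "reflecting whether the variable moderated treatment effects". Neither that section nor 7.16.2.2 says whether product terms enter the imputation.

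**Expected loss.** Section 7.15.4 states: "we expect roughly 30-50% attrition by the final follow-up timepoint". The same section and 7.16.2.1 also give a figure of about 10% of data points.

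**Data available.** Therapists complete a CGI-I after each session or call "to characterize their session-by-session judgement of the extent of treatment-related improvement" (7.6.2). Weekly logs record attendance and homework, and back-end usage is captured for the online arm (7.6.3). Caregivers, and youth aged 8 or over, both complete PROMIS and CALIS (7.6.1).

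**The concern.** For missing outcomes, a mixed model already uses every observed wave under a missing-at-random assumption. Imputing those outcomes from the same variables adds little. The gain comes from variables outside the analysis model that predict both dropout and outcome. The plan collects several and commits to none.

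At stake is the longer-term part of Aim I. Section 2.5 says attrition can be high in self-administered online care, and therapist contact differs greatly between arms. If poorly engaged families leave the online arm for reasons that the imputation cannot see, that arm looks better at Week 52 than it is. Leaving the auxiliary set and the product terms unstated also allows them to be chosen after the data are seen.

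**Working it through.** **1. Inputs from the documents.** N = 300, 150 per arm; four waves; ICC 0.5 (7.16.1); 30-50% attrition by final follow-up (7.15.4). This leaves 300 x 0.70 = 210 down to 300 x 0.50 = 150 families observed at Week 52. The missing-data section itself gives only about 10%. Even if 10% were lost at each of three post-baseline waves, 1 - 0.9^3 = 27%, which is below the range. The imputation paragraph gives no numerical result to reproduce.

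**2. Inputs assumed.** The documents give neither the strength of any auxiliary nor a dropout model. A standardised engagement variable E is assumed to drive dropout and to shift the outcome by 0.2, 0.4 or 0.6 per SD of E, where the outcome SD without E is about 1. Week 52 missingness is 30, 40 or 50% overall.

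**3. Arm contrast.** Large-sample simulation (400,000 subjects per cell) with Week 52 imputed by stochastic regression. Entries are bias in SD units; a negative value flatters the online arm.

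| Dropout scenario | Arm + covariates | + earlier waves | + E and E x arm |
|---|---|---|---|
| Same mechanism in both arms | about 0 | about 0 | about 0 (all within 0.006) |
| E 0.5 SD lower online, same slope | -0.01 to -0.04 | -0.01 to -0.02 | 0.00 |
| E drives dropout online only | -0.06 to -0.23 | -0.04 to -0.10 | 0.00 (within 0.005) |

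The third row in detail (arm + covariates / + earlier waves):

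| Shift per SD of E | Missing 25% vs 35% | 35% vs 45% | 45% vs 55% |
|---|---|---|---|
| 0.2 | -0.057 / -0.037 | -0.071 / -0.042 | -0.085 / -0.048 |
| 0.4 | -0.108 / -0.060 | -0.132 / -0.067 | -0.160 / -0.085 |
| 0.6 | -0.152 / -0.066 | -0.186 / -0.081 | -0.233 / -0.100 |

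Earlier waves roughly halve the bias at moderate to strong shifts. The auxiliary removes it.

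**4. Hand check of the dependence on unequal rates.** With probit dropout and baseline as the only earlier wave, bias = rho x r x residual SD x (difference between arms in the mean selection shift). Assume slope 1 (rho = 0.71) and baseline correlation 0.5 (residual SD 0.866). At 50% versus 30% missing the bracket is 0.798 - 0.497 = 0.301. The bias is then 0.09, 0.11 and 0.13 SD for r = 0.5, 0.6 and 0.7. At 45% versus 35% it is about 0.05 (r = 0.5) and 0.06 (r = 0.7). At equal rates it is 0.

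**5. Scale.** The 60 per group in 7.16.1 does not follow from the printed formula, which gives 2 x (1.96 + 0.84)^2 = 15.7 two-sided and has no effect-size term. Sixty implies d = sqrt(15.7/60) = 0.51. A bias of 0.10 SD is about a fifth of that.

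**6. Product terms.** Values imputed without an interaction carry none, so the surviving share at Week 52 is roughly 1 minus the missing fraction.

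| Missing | 1 - fraction | Simulated, term omitted | Simulated, term included |
|---|---|---|---|
| 30% | 0.70 | 0.68-0.72 | 0.98-1.03 |
| 40% | 0.60 | 0.58-0.61 | 0.98-1.03 |
| 50% | 0.50 | 0.47-0.52 | 0.98-1.03 |

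Adding E without the product term leaves the shrinkage unchanged.

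**The case against.** Several stronger readings are tempting, and the documents do not support them.

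- **Imputation from demographics alone.** A reader might infer this from the rule, but the text does not say only. Imputation is tied to each analysis model, and the multilevel version would probably use the same child's other waves and the model's arm and time terms. Baseline variables that differ between arms also enter. This objection stands, and it favours the smaller range, 0.04-0.10 SD, for PROMIS and CALIS.
- **30% loss in one arm and 50% in the other.** Section 7.15.4 gives one overall range. Section 2.5 gives no figure by arm. Bias needs an arm difference in dropout that no passage shows.
- **Missing auxiliaries shrink moderator effects.** They do not. Shrinkage arises only if product terms are omitted, which the plan leaves open. Because imputation is done per model, they may well be meant to be included.
- **30-50% loss applied to PARS and satisfaction.** These are analysed at posttreatment; the figure is for the final follow-up.

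Two further points are fair. Imputation still helps with missing covariates: resource insecurity is caregiver-reported (7.6.4), yet adolescents can be randomised without a caregiver baseline (7.11). Also, families who stop treatment are still assessed (7.8.2, 7.15.4), so poor attendance need not mean a missing outcome. Neither point supplies the missing specification.

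**Conclusion.** The concern holds in a limited form. The stated rule names no auxiliary variable, so for missing outcomes it adds little to the likelihood analysis and leaves collected predictors of dropout and outcome unused.

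The Week 52 arm contrast could be biased by about 0.04-0.10 SD with earlier waves used, or 0.06-0.23 SD with arm and covariates only. This rests on assumed outcome shifts of 0.2-0.6 per SD of engagement and on engagement driving dropout in one arm only. It is about 0 if dropout rates and mechanism match. The figures describe a Week 52 difference, not the slope on log time that the plan fits.

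The PARS responder and satisfaction models are the most exposed, because baseline PARS and midtreatment satisfaction are not among their listed covariates. No size can be given for them, since posttreatment loss is not separately stated.

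The silence on product terms is a separate gap. If they were omitted, 0.47-0.72 of a true Week 52 moderator effect would survive at 30-50% missing. Shrinkage of the three-way time term would depend on missingness at every wave. The plan should be amended, but nothing here shows that the trial's contrast will be biased.

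**What to change.** In 7.16.2.2, state that every imputation model contains:

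- Treatment Condition and, for repeated outcomes, Time and Treatment x Time;
- all available waves of the outcome, including baseline PARS and midtreatment satisfaction for the single-level models;
- each product term tested, or else use Blimp's model-based imputation of the analysis model;
- a pre-specified auxiliary set: other-informant PROMIS and CALIS, last therapist CGI-I, proportion of planned sessions or calls attended, and treatment-withdrawal status.

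Impute separately by arm or with arm interactions. Completion means 10 sessions in one arm and 4 calls in the other, CGI-I is rated about weekly or about every two weeks, and module usage exists only online. Reconcile the 30-50% and 10% figures, and give expected loss by wave.

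**Cost.** SAP wording and larger imputation models, with no new data or software. Some auxiliaries will themselves be missing: self-report for 7-year-olds, CGI-I for families who never start, and both informants' scores when a whole assessment is missed. The change addresses only dropout that is explained by measured variables.

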7.16.3 Covariates

Covariates for each model will include site, language of care, youth age, youth gender, youth race, youth ethnicity, and family resource insecurity (see Measures)

7.16.4 Primary analyses: Comparative effectiveness analyses. For primary analyses on continuous outcomes that were measured across the 4 major timepoints (e.g., caregiver- and youth-reports on the PROMIS Anxiety Scale, CALIS), mixed models of change¹⁴⁴ will be run separately for each outcome. Mixed models are preferred for longitudinal designs because they allow for individual estimates of change and have robust power in the presence of missing data and attrition.^{145,146} Covariates for each model will include site, language of care, youth age, youth gender, youth race, youth ethnicity, and family resource insecurity (see Measures), and any other baseline variables found to significantly differ across participants in the two conditions. The random effects of intercept (reflecting individual variation in mean outcome level) will be assessed. The fixed effects of Treatment Condition, Time, and the Treatment \times Time interaction will be analyzed in the prediction of change. We will examine non-linear models of change (i.e., log transformations of Time), which afford examination of symptom trajectories across time that are not gradual and incremental (e.g., steep improvements during initial weeks of treatment, followed by a slowing down of improvements toward the end of treatment, and then relative stability across the follow-up time interval). To aid interpretation of the meaningfulness of between-group differences, Cohen's d 's will be computed for each continuous outcome on model means at post and follow-up.

For primary analyses on the dichotomous categorical outcomes PARS Treatment Responder Status at posttreatment, baseline PARS scores will be examined for each participant to determine their individual thresholds for classification as Treatment Responders (i.e., 35% PARS score reduction). These thresholds will be used to classify each participant's statuses as posttreatment. Logistic regression models will examine Treatment Condition (along with the study covariates) as a predictor of Treatment Responder Status and Remission Status at post. For primary analyses on continuous outcomes of Treatment Satisfaction at post, linear regression models will examine Treatment Condition (with the study covariates) as a predictor of caregiver- and youth-reported posttreatment satisfaction.

7.16.5 Heterogeneity of treatment effects. For Aim II analyses (heterogeneity of treatment effects) predictor and moderator terms will be added to the models predicting youth anxiety severity that were outlined above. For study covariates being considered as predictors/moderators (e.g., language of care, youth age, youth gender, youth race, youth ethnicity, and family resource security), this will entail only adding interaction terms, as the main effects of these variables will already be in the models. For the additional variables considered as treatment moderators that are not already included as model covariates (e.g., caregiver nativity) this will entail adding main effects and interaction terms to the models. For each model examining heterogeneity of treatment effects, the relevant terms of interest will be the 2-way interaction of Variable \times Time (reflecting whether the variable uniformly predicted change across the two treatments) and the 3-way interaction of Variable \times Treatment Condition \times Time (reflecting whether the variable moderated treatment effects; i.e., whether the variable predicted differential response across the treatments). As with the Aim I comparative effectiveness analyses, log transformations of Time will be entered to consider non-linear models of change. Significant interactions will be followed up with post-hoc probing on subgroups to clarify the nature and direction of interaction, and results will be plotted for visual depiction.

7.16.6 Facilitators and barriers. Descriptive statistics will be run for models exploring facilitators and barriers to care and implementation (Aim III). These models will include the same covariates as outlined for Aim I and Aim II analyses. Treatment Condition will be added as a predictor in models comparing whether facilitators and barriers differ between the two treatment comparators.

7.16.7 Interim Analysis. Interim descriptive data will be summarized each year for the investigative team. Our team will conduct analyses as required for the reporting of findings in peer-reviewed manuscripts and at conferences, and will assist with editing and writing manuscripts.

8 – Ethical Considerations

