4.1 Primary Objective

The objective of Aim 1 (*Comparative Effectiveness*) is to compare the acute and long-term effectiveness of Therapist-Led CBT (telehealth, office-based, or hybrid) vs Guided Online CBT (with minimal clinician support) for treating youth anxiety identified in pediatric healthcare. It is hypothesized that youth in both conditions would show significant curvilinear improvements over time characterized by relatively steep improvements during the beginning and middle of the treatment phase, followed by a slowing down of improvements toward the end of treatment and then relative stability across the follow-up time interval. Comparative effectiveness analyses will

compare differences in outcome slopes across the two conditions. Aim 1 focuses on the following primary treatment outcomes across the comparators: family-rated anxiety severity, family-rated anxiety-related life impairment, independently rated treatment responder and anxiety remission status, family perceived effectiveness, and family satisfaction with care. Data on a range of secondary outcomes are also collected.

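### The PROMIS and CALIS mixed models name only a child random intercept although the tested effect is a difference in slopes; unless children's slopes are identical and correlations stay constant over 52 weeks, the Treatment × Time standard errors will generally be too small.

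*Combined protocol and SAP*

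**What the plan says.** Section 4.1 states that the comparative analyses will "compare differences in outcome slopes across the two conditions". Section 7.16.4 implements this for outcomes measured at all four timepoints, with PROMIS Anxiety and CALIS (caregiver and youth reports) as its examples:

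- Fixed effects: "The fixed effects of Treatment Condition, Time, and the Treatment" × Time interaction.
- Form of Time: "We will examine non-linear models of change (i.e., log transformations of Time"), so Time enters as a continuous term.
- Random effects: "The random effects of intercept (reflecting individual variation in mean outcome level) will be assessed". No other random effect is named.
- Reason for choosing mixed models: "because they allow for individual estimates of change and have robust power in the presence of missing data and attrition".

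Section 7.16.5 builds the Aim II models by adding Variable × Time and Variable × Treatment × Time terms to the anxiety-severity models, the latter "reflecting whether the variable moderated treatment effects". Section 7.16.2.2 names the software ("lme4 for multilevel models") and multilevel multiple imputation, but gives no residual correlation structure and no robust standard errors. No section names a random slope, rules one out, or gives a rule for adding one.

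**The concern.** A model whose only child-level random effect is an intercept assumes two things: children in the same arm with the same covariates share one true rate of change, and any two visits are equally correlated whether they are 8 or 52 weeks apart. If either fails, the model-based standard error of a slope difference is computed from the wrong variance. With four waves it counts only one third of the between-child slope variance.

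The stated model also does not deliver the property for which it was chosen. A random-intercept model gives every child in an arm the same estimated change, so it does not provide the individual estimates of change on which section 7.16.4 relies.

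Treatment × Time is the primary test for four outcome-by-informant measures (PROMIS and CALIS, each by caregiver and youth), and the Aim II interaction tests inherit the same structure. Section 7.16.1 assumes a family-wise error rate of .05; that cannot be relied on if the component tests exceed their nominal level. This is variation between children in slope, and is separate from any clustering by therapist or site.

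**Working it through.** **Inputs from the documents.** Four waves with target weeks 0, 8, 20 and 52 (section 7.1; mid- and posttreatment can fall earlier); 150 per arm, α = .05 and ICC = .5 (section 7.16.1); 30–50% attrition by final follow-up and about 10% of data missing per timepoint (section 7.15.4).

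**Assumptions.** Two-sided tests (sidedness is not stated); Time = log(1 + week); outcome variance scaled to 1, so that ICC .5 gives residual variance σ² = .5; a range for the between-child slope variance τ², for which the documents give no figure.

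**The plan's own figures.** Design effect: 1 + (4 − 1) × .5 = 2.5, and 60 × 2.5 = 150 per arm. The Aim II sensitivity figure of 0.068 reproduces as 0.0675 (as an f) for the repeated-measures within-between interaction with N = 300, four measurements and a common correlation of .5. Both calculations use one constant correlation. That is the covariance under which a random-intercept model is correct, with α = .05.

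**Closed form, complete data.**

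1. log(1 + {0, 8, 20, 52}) = 0, 2.197, 3.045, 3.970; mean 2.303; sum of squares about the mean S = 8.645.
2. True variance of the Treatment × Time estimate: (2/n)(σ²/S + τ²).
3. Variance reported by the random-intercept fit: (2/n)(σ²/S + τ²/3). The slope variance enters the within-child mean square spread over m − 1 = 3 degrees of freedom.
4. With r = τ²S/σ², true/reported variance = (1 + r)/(1 + r/3), and actual α = 2[1 − Φ(1.96/√ratio)]. Slope reliability is r/(1 + r). The SD of true Week 52 change is 3.970 × √τ².

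| Slope reliability | r | SD of true Week 52 change | Variance ratio | SE understated by | Actual α |
|---|---|---|---|---|---|
| 0 | 0 | 0 | 1.000 | 0% | .050 |
| .20 | .25 | 0.48 | 1.154 | 7% | .068 |
| .33 | .50 | 0.68 | 1.286 | 12% | .084 |
| .50 | 1.00 | 0.95 | 1.500 | 18% | .110 |

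Example, r = .5: τ² = .5 × .5/8.645 = .0289. Reported variance is (2/150)(.0578 + .0096) = .00090; true variance is (2/150)(.0578 + .0289) = .00116; the ratio is 1.286.

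**Under the planned attrition.** Simulation of a REML random-intercept fit with no treatment effect: 150 per arm, 2,000 trials per cell, dropout rising to 30% or 50% by the last wave plus 10% intermittent missingness after baseline.

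| Slope reliability | Complete | 30% attrition | 50% attrition |
|---|---|---|---|
| 0 | .052 | .050 | .053 |
| .2 | .070 | .060 | .062 |
| .4 | .092 | .092 | .081 |
| .5 | .107 | .099 | .093 |

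Dropout was unrelated to outcome, and the simulation had no covariates, site effects or imputation.

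**Correlations that fall with lag, complete data.** Correlations of .6/.45/.30 at one, two and three visits apart give α = .105; a mild decline of .55/.50/.45 gives .069.

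**Selection at entry.** Suppose the PROMIS threshold halves the baseline variance. With no slope variance, α falls to .039. With the three non-zero slope variances in the first table it is .059, .076 and .104.

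**The case against.** Four objections have force.

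- **No slope variance is given.** A reader might infer that the standard errors are too small and that type I error certainly exceeds .05. The documents do not support that: under the plan's own constant correlation of .5 the intercept-only model is right and α is .05. This stands, and the point is conditional for that reason. It does not make the model safe, because a constant correlation used for planning is no evidence that correlations hold over 52 weeks.
- **The text is silent on a random slope.** A reader might infer that one is excluded. It is not, and the stated reason for using mixed models may mean that one was intended. That also stands. But an analyst following section 7.16.4 as written would fit the intercept-only model; otherwise the covariance of the primary model is left to a choice made after seeing the data.
- **The direction is not guaranteed.** Selection on baseline PROMIS restricts baseline variance and can make the test conservative if slopes do not vary. This stands as an offset, but under the halving assumed above the error rate stays above .05 once slopes vary in the range considered.
- **The upper end is demanding.** At slope reliability .5, with independent intercept and slope, Week 52 variance is 1 + .0578 × 3.970² = 1.91 against 1 at baseline, which no longer matches an ICC of .5. At reliability .2 it is 1.23.

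It can also be said that Aim II allows for different rates of change through fixed interactions with measured variables, so it does not by itself presuppose random slopes. That is true of the Aim II models. The Aim I models, however, carry those covariates as main effects only (section 7.16.5 adds the interactions), so any real Variable × Time effect remains there as unmodelled slope variation.

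**Conclusion.** The point holds in conditional form. The stated random-effects structure does not match a slope comparison, and nothing else specified in the plan would correct the standard error. Unless true slopes are identical across children and correlations are constant over 52 weeks, the standard error of Treatment × Time, and of the Aim II Variable × Time and three-way terms, will generally be understated. For an assumed slope reliability of .2 to .5, two-sided type I error is about .07 to .11 with complete data and about .06 to .10 under the expected attrition. Restriction of baseline variance at entry would reduce these figures somewhat.

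The scope is limited to the PROMIS and CALIS models and the Aim II models built on them. A reader might extend the point to every primary outcome, but PARS responder status and treatment satisfaction are analysed by ordinary logistic and linear regression at posttreatment and are untouched. With complete, balanced data only the standard error is at issue, not the Treatment × Time point estimate.

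**What to change.** In sections 7.16.4 and 7.16.5, pre-specify a child random intercept plus a random slope for whichever Time term is used, (1 + Time | child), in every model that tests a Time interaction. State the fallback in advance: if the fit is singular, report child-level cluster-robust (CR2) standard errors and do not revert to model-based intercept-only errors. An unstructured covariance by visit is an acceptable alternative, with its software named. In section 7.16.2.2, carry the same random effects into the multilevel imputation model.

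The cost is a sentence or two in the SAP and one model term, slightly wider intervals where slopes do vary, and occasional convergence handling. If slopes do not vary, almost nothing is lost: with complete, balanced data the random-slope test essentially compares per-child slopes, and the critical value moves only from 1.963 (300 × 3 − 2 = 898 degrees of freedom) to 1.968 (300 − 2 = 298).
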